#### **6.4.3.2 Secondary Objectives Analyses**

Analysis will be conducted utilizing an independent two sample t-test.

#### **6.4.3.3 Analysis of Subject Characteristics**

We will summarize baseline and demographic characteristics utilizing standard descriptive summaries (means and standard deviations for continuous variables such as age and percentages for categorical variables gender).

## 7 – Study Administration

### 7.1 Ethical Considerations: Informed Consent and HIPAA Authorization

A waiver of informed consent (usual care group).

A waiver of written documentation of consent (intervention group) and HIPAA authorization (all participants) will be obtained for this study. Verbal consent via telephone will be obtained for intervention group participants who are willing to complete the post-intervention interview.

### 7.2 Institutional Review Board (IRB) Review

The protocol and all participant materials will be submitted to the IRB for approval. Any amendment to the protocol will be sent to the IRB for approval before the changes are implemented to the study. The IRB will be made aware of any reportable events and unanticipated problems.

### 7.3 Subject Privacy, Confidentiality & Data Management

The collection of personal patient information will be limited to the amount necessary to achieve the aims of the research, so that no unneeded sensitive information is being collected. Only study personnel as listed on the IRB will have access to study data. Patient identifiers that will temporarily be accessed/reviewed include name, medical record number, date of birth, phone number, address, height, weight, smoking status, and CRC screening history. Electronic study data will be stored on a securely managed (MCIT) network drive and in REDCap, with password-protected access limited to trained, authorized study personnel. It is not expected that paper documents will be generated in association with this study, however, any hard copy documents will be kept in a locked cabinet in the PI's office. Electronic data will be exported into excel file format (password protected) and utilized for data analysis. De-identified data will be sent to a biostatistician for statistical analysis.

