#### 5.2.2 Secondary and Exploratory Outcome Variables

1) Completion of colonoscopy for individuals with a positive fecal immunochemical test at 6 months.

2) Determination of factors associated with non-adherence to initial fecal immunochemical testing or colonoscopy, and to completion of colonoscopy for those with positive FIT.

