#### **5.3.3 Exclusion Criteria**

- Age younger than 45 years old or greater than 75 years old
- Up-to-date with colorectal cancer screening (FIT within 1 year or colonoscopy within 10 years)
- History of colorectal cancer, inflammatory bowel disease or colorectal polyps
- No address or phone number on file
- FIT test ordered within 6 months

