#### **6.1.2 Method of Assignment/Randomization**

The study biostatistician will randomize 50 eligible patients to proactive outreach and 50 eligible patients to usual care, stratified by age and biological sex. Proactive outreach patients will be blind to the presence of an alternative group assignment and "usual care" patients will be unaware of group assignment altogether.

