### **6.3.3 Screening**

Screening for participant eligibility will be performed through the research team accessing patient charts through the Flatbush FHC's EMR (Epic) and applying the inclusion and exclusion criteria previously stated.

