### **6.3.4 Recruitment, Enrollment and Retention**

Patients will be identified for inclusion in the study via accessing the Flatbush FHC EMR (Epic) and applying the inclusion and exclusion criteria previously mentioned. We will work with DataCore to obtain an initial list of eligible patients once, at the beginning of the study. The PI and study coordinators will be the only research staff with access to the list. The list will contain the following information about the eligible patients: MRN, full name, date of birth (or age), address, phone number(s), email addresses, biological sex, race, ethnicity, height/weight (or BMI), smoking status, and primary care physician's name. Data for the patients that will not be included in the study will be deleted from the electronic list provided by DataCore at the end of the study. No information will be retained about these patients.

After the mailed intervention process is complete, data regarding colorectal cancer screening will be obtained for the control group patients. This will include whether colonoscopy, FIT, or other screening tests for colorectal cancer were completed during the study period. Approved waiver of consent and HIPAA authorization for this patient group will allow this information to be collected directly from Epic by the study team.

The primary care physicians at Flatbush FHC have been notified that their intervention group patients will be contacted directly by the study team regarding this mailed CRC screening effort. All letters from the FHC (initial and final) will contain their electronic signature. These patients will receive the Study Information Sheet as part of the initial FIT kit mailing (first contact). If they decide to opt out, only de-identified data will be retained in REDCap for audits, summaries, and reporting purposes.

Subjects in the usual care group will not be approached or notified of their enrollment in the study.

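### Prior colorectal cancer screening history is reviewed at eligibility, but the plan does not specify it as a baseline descriptor, a covariate or a candidate factor for non-adherence

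*Combined protocol and SAP*

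**What the plan says.** Section 5.3.3 excludes anyone "Up-to-date with colorectal cancer screening (FIT within 1 year or colonoscopy within 10 years"), and 6.3.3 says eligibility is checked by "accessing patient charts through the Flatbush FHC's EMR (Epic) and applying the inclusion and exclusion criteria previously stated". Section 7.3 confirms that screening history is looked at: its list, introduced by "Patient identifiers that will temporarily be accessed/reviewed include name, medical record number", ends with "height, weight, smoking status, and CRC screening history".

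The plan does not name the item again as a design or analysis variable:

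- The eligible-patient list in 6.3.4 runs to "biological sex, race, ethnicity, height/weight (or BMI), smoking status, and primary care physician's name" and has no field for past screening.
- Randomisation in 6.1.2 is "stratified by age and biological sex" only.
- Sections 6.4.1, 6.4.3 and 6.4.3.1 give an independent two-sample t-test without covariates for the primary outcome. Section 6.4.3.2 gives the same test for the secondary objectives.
- The baseline summary in 6.4.3.3 is described as "means and standard deviations for continuous variables such as age and percentages for categorical variables gender".
- Secondary outcome 2 in 5.2.2 is "Determination of factors associated with non-adherence to initial fecal immunochemical testing or colonoscopy", and likewise to colonoscopy after a positive FIT. No candidate factor or model is named.

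**The concern.** Every participant is due or overdue, but that group can mix patients with no screening on record and patients whose screening has lapsed. Whether someone has been screened before is an obvious candidate predictor of whether they complete screening in the next 6 months. The team has the chart open on this very subject when it decides eligibility.

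Two things are at stake. First, with 50 patients per arm and stratification on age and sex only, the arms can differ by chance in the previously screened share. As specified, nothing would show such a difference or correct for it. Second, secondary outcome 2 sets out to find factors associated with non-adherence without naming any. If prior screening is defined only after outcomes are known, its choice is open to the charge of post hoc selection.

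**Working it through.** **No figure to reproduce.** Section 6.4.2 bases the sample size of 100 on feasibility and gives no power, effect size or expected completion rate. The 48-55% in section 3.1 is the centre's overall screening rate, not 6-month completion among due or overdue patients. Only the 50 per arm below comes from the documents; all rates are assumptions.

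**Precision.** Let f be the share with a past screen on record, p1 and p0 the completion rates with and without one, and p = f·p1 + (1−f)·p0. The variance explained by this binary field is

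R² = f(1−f)(p1−p0)² / [p(1−p)],

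the adjusted standard error is the unadjusted one times √(1−R²), and the gain is worth about 100·R²/(1−R²) extra patients.

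- *Central case*, f = 0.40, p1 = 0.40, p0 = 0.15: p = 0.25; R² = 0.24 × 0.0625 / 0.1875 = 0.08; √0.92 = 0.959, so the standard error falls by 4%; 100 × 0.08/0.92 = 8.7 patients.
- *High case*, f = 0.40, p1 = 0.50, p0 = 0.15: p = 0.29; R² = 0.24 × 0.1225 / 0.2059 = 0.143; √0.857 = 0.926, about 7% lower; 16.7 patients.
- *Lower case*, f = 0.30, p1 = 0.50, p0 = 0.35: p = 0.395; R² = 0.21 × 0.0225 / 0.2390 = 0.020; 1% lower; 2.0 patients.

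A second grid set control completion at 10-30%, a 20-point effect, f = 0.2 or 0.5, and a contrast of 10-30 points between patients with and without a past screen, dropping cases that imply a negative rate. It gives R² from 0.007 to 0.112 and a standard error 0.3% to 6% lower. At its most favourable point (20% v 40% completion, f = 0.5, 30-point contrast):

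- Unadjusted 95% half-width: 1.96 × √[(0.16 + 0.24)/50] = 17.5 points.
- Adjusted: 1.96 × √[(0.40 − 2 × 0.25 × 0.09)/50] = 16.5 points.
- Power on the same normal approximation rises from 61% to 66%.

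Together these cases span R² of about 0.01-0.14. That is the range of the cases worked, not a bound: lower completion among patients with no past screen would raise it.

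**Chance imbalance.** Taking the two arm counts as independent Binomial(50, f), the probability that they differ by 5 patients (10 points) or more is 26% at f = 0.2, 36% at f = 0.4 and 37% at f = 0.5. A 10-point gap moves the unadjusted difference by 0.10 × (p1−p0): 1 to 3 points for contrasts of 10 to 30 points, and 2.5 points in the central case. For scale, the unadjusted standard error at 25% completion is √(2 × 0.25 × 0.75/50) = 8.7 points, so 2.5 points is about 0.3 of a standard error.

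**Overlap with age.** These figures treat prior screening as independent of age and sex. Section 2.1 says 45-49 year olds were added to the recommendation only recently, so prior screening may track age. Part of both the imbalance and the gain would then already be taken up by the age strata.

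**The case against.** The strongest case against is that nothing in the plan is contradicted or invalid and the gain is small. Several stronger readings are tempting, and the documents do not support them.

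- *That the history is excluded from the baseline table and the non-adherence analysis.* The wording in 6.4.3.3 gives age and gender as examples, and 5.2.2 lists no factors from which one could be missing. The finding is that the item is not specified.
- *That it will be discarded.* The temporary access in 7.3 covers the whole list, including date of birth, yet age is to be summarised. The list in 6.3.4 is an initial eligibility extract, not a list of analysis variables. Section 7.5 says data are collected during eligibility screening and retained for 10 years. Retention of this item is unclear, not ruled out.
- *That the unadjusted comparison is biased.* Chance imbalance under randomisation is already reflected in the unadjusted standard error.
- *That balance is lost.* Adjustment corrects for an imbalance after the event. Only the allocation scheme can reduce it.
- *That the field costs nothing.* The exclusions need only a FIT within 1 year, a colonoscopy within 10 years and a FIT order within 6 months. A field covering any screening ever recorded may need a longer look-back, and 7.3 commits to collecting no more than is needed.

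The objection that every rate is assumed also stands. It limits the size of the claim. It does not remove the gap: a directly relevant baseline item is reviewed, the plan assigns it no analytic role, and a stated secondary outcome has no named factors.

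**Conclusion.** The point holds as a modest, low-cost improvement in specification. Screening history is reviewed to settle eligibility, but the plan gives it no stated place in the baseline table, the primary analysis or secondary outcome 2.

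The precision gain would be small and would not change what a feasibility-sized pilot can conclude. The case rests at least as much on reporting whether the arms are comparable on this item and on fixing a candidate factor for secondary outcome 2 in advance. The sizes depend on assumed previously screened shares of 20-50% and contrasts of 10-35 points, with no overlap with age or sex. The documents supply none of these.

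**What to change.** Before randomisation, derive and keep one field for all 100 patients: prior FIT or colonoscopy on record within the look-back used for eligibility, or none on record. State that look-back as a single period for both tests. If each test were read only over its own exclusion window, everyone with a recorded screen would already be excluded and the field would be constant. With a common 10-year period, for example, a FIT more than 1 year old would count as lapsed screening. Then:

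- add the field to the data list in 6.3.4 and pass it to the biostatistician with the de-identified data;
- show it by arm in 6.4.3.3;
- name it as a candidate factor for secondary outcome 2;
- in 6.4.3.1, prespecify a risk difference adjusted for this field together with age and sex, the stratification factors, and report it with the unadjusted difference.

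The cost is one field to define and retain, and a protocol amendment with IRB approval (7.2). No patient contact or visit is added. Some patients will be misclassified: none on record is not the same as never screened, since past screening may have taken place elsewhere (6.3.5 allows colonoscopy at other facilities). Misclassification would weaken the field as a predictor and reduce the gain.

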### 7.4 Deviations/Unanticipated Problems

Any unanticipated problems will be reported promptly to the IRB (within one business day of discovery for serious adverse events), within 7 business days of discovery for all other unanticipated problems.

### 7.5 Data Collection

Data will be collected at the beginning the study during the initial eligibility screening process as well as ongoing throughout the intervention period in order to ascertain FIT testing and/or colonoscopy completion results. Data will only be accessed by trained, authorized study personnel. Data will be retained for the next 10 years for use in future studies following the completion of this pilot study.

## **7.6 Data Quality Assurance**

All research coordinators and study personnel will be trained by the primary investigator on both the intervention and data collection process. The study will be continuously monitored on a monthly basis by the study team. Standardized templates for proactive outreach letters will be utilized during the study. Statistical analysis will be performed by a professional biostatistician.

## **7.7 Study Records**

Study records include subject medical records including FIT testing/colonoscopy results, outreach attempts and outcomes, and any survey results collected and interview transcripts.

## **7.8 Access to Source**

Source documents will be obtained from the Flatbush Family Health Center's electronic medical record (NYU Langone Health's Epic system). All study personnel listed on the IRB will have access to the study documents.

## **7.9 Data Storage / Security**

Electronic study data will be stored on a secure NYULH MCIT-managed network shared drive and in REDCap. All hard copy documents will be kept in a locked cabinet in the PI's office. Electronic data will be exported into excel file format (password protected) and utilized for data analysis. De-identified data will be sent to a biostatistician for statistical analysis.

## **7.10 Retention of Records**

Study documents will be retained for the longer of 3 years after close out or 5 years after final reporting/publication. These documents should be retained for a longer period, however, if required by local regulations. No records will be destroyed without the written consent of the sponsor, if applicable. It is the responsibility of the sponsor to inform the investigator when these documents no longer need to be retained.

## **7.11 Future Use of Stored Data**

Data will be maintained for 10 years following the pilot study in order to be utilized in future studies. Study data will be stored in REDCap and on a secure NYULH MCIT-managed network shared drive. Access to the dataset for any future research will require separate IRB approval. If any information is shared with external interested site(s), data set agreements with NYU LANGONE will be established.

Transcripts from the patient interview audio recordings will be de-identified and will be used to tailor and improve possible future proactive CRC screening efforts.

Study data may be used to inform future funding proposals. The purpose of other possible future research is unknown at this time.

## **7.12 Study Monitoring**

The principal investigator will monitor the study to ensure that it is completed in accordance with the protocol and that the data are valid. In order to ensure this, the study will be reviewed on a monthly basis by the principal investigator and study team.

## **7.13 Data Monitoring Plan**

Our study involves minimal risk and thus does not require a data monitoring plan.

## **7.13 Study Modification**

The study protocol will be updated with any study modifications and submitted to the IRB for approval.

## **7.14 Study Discontinuation**

Given the benign nature of the study intervention, we do not foresee the study being discontinued for any reason.

## **7.15 Study Completion**

The anticipated completion date of the study will be approximately one year after commencement of the intervention period. We will notify the IRB upon completion of the study.

## **7.16 Conflict of Interest Management Plan**

There are no actual or perceived conflicts of interest for our study.

## **7.17 Funding Source**

The study is funded by NCI (p20 SPORe pilot grant).

